## 7.2. Flow-chart

Table 5: Flow chart showing the connection between visits, assessments, and procedures

	PER-FORMED BY	SCREENING VISIT	BASELINE VISIT	PHONE CALL VISIT	PHONE CALL VISIT	PHONE CALL VISIT	TERMINTION VISIT
VISIT	-	V0	V1	V2	V3	V4	V5
WEEK	-	WEEK 0	WEEK 0	WEEK 1	WEEK 2	WEEK 3	WEEK 4
VISIT WINDOW	-	-	-3DAYS	±1 day 7 DAYS	±1 day 14 DAYS	±1 day 21 DAYS	+3 days 28 DAYS
GENERAL							
Introduction to the investigation and review of Informed Consent Form/Subjects Information Form	Investigator or delegate	X					
Check of in- and exclusion criteria	Investigator or delegate	X	X				
Informed Consent Signed	Investigator and Subject		X				
Allocation of subject number	Investigator or delegate		X				
Collect Baseline information	Investigator or delegate		X				

	PER-FORMED BY	SCREENING VISIT	BASELINE VISIT	PHONE CALL VISIT	PHONE CALL VISIT	PHONE CALL VISIT	TERMINITION VISIT
Review of concomitant medication	Investigator or delegate		X	X	X	X	X
Assess AEs/ADEs/SAEs/SADES, Device Deficiencies and Protocol Deviations	Investigator or delegate		X	X	X	X	X
QUESTIONNAIRES AND ASSESSMENTS							
ISC-Q assessment	Subject		X				X
InCaSa assessment	Subject		X				X
Perception assessment	Subject		X				X
Evaluation of catheterization since last visit	Subject			X	X	X	X
Preference	Subject						X
Reason for drop out if Termination Visit is performed prior to 28 test days	Subject						X
PROCEDURES							
Urine dipstick for haematuria, leucocytes, and nitrite	Investigator or delegate		X				X
Urine dipstick for hematuria, leucocytes, and nitrite	Subject			X	X	X	
Urine dipstick (female subjects of childbearing potential)			X				
Remind subject of ending use of CLINY catheter after 28 days of use regardless scheduled date of Visit 5	Investigator or delegate			X	X	X	
Reminder of instruction for CLINY Self-Catherization set	Investigator or delegate			X	X	X	
Insurance of subject's compliance with CIP	Investigator or delegate		X	X	X	X	X
Instruct the subject in use of weekly urine dipstick form	Investigator or delegate		X				
Review of weekly urine dipstick form for completeness and compliance							X

	PER-FORMED BY	SCREENING VISIT	BASELINE VISIT	PHONE CALL VISIT	PHONE CALL VISIT	PHONE CALL VISIT	TERMINTION VISIT
Instruct the subject in use of CLINY accordingly the IFU	Investigator or delegate		X				
Distribution of CLINY Self-Catheterization set and investigational supplies	Investigator or delegate		X				
Schedule Baseline Visit (V1) Unless performed the same day as V0	Investigator or delegate	X					
Schedule Visit 2 (Phone Call) 7 days after Visit 1 +/-1 day	Investigator or delegate		X				
Schedule Visit 3 (Phone Call) 14 days after Visit 1 +/-1 day	Investigator or delegate			X			
Schedule Visit 4 (Phone Call) 21 days after Visit 1 +/- 1 day	Investigator or delegate				X		
Schedule Termination Visit V5 (28 days after Visit 1)	Investigator or delegate					X	
Complete eCRF	Investigator or delegate		X	X	X	X	X
Collect CLINY Self-Catheterization set	Investigator or delegate						X
Send CLINY Self-Catheterization set for Laboratory assessments and analysis	Investigator or delegate						X
Perform device accountability	Investigator or delegate		X				X

### 7.3. Case Report Forms

All assessments and observations throughout the investigation for each subject must be carefully recorded in an electronic CRF (eCRF). Details about data capture can be found in section 11 (Data Management).

CRFs will be completed by the investigator or delegate, who have signed the Site Personnel Signature and Delegation List and Clinical Investigation Training Log. The delegated site personal will be required to complete e-learning prior to system access. After completed training delegated personal will receive credentials.

It is the responsibility of the investigator that all data, all measurements, and observations are entered promptly and correctly and preferably immediately after the subject has been at site or after a phone call. In case this is not possible the data should be entered no later than 7 days after the visit / procedure.

#### **7.4. Concomitant treatment**

Concomitant medication taken from the time of consent through the investigation until termination will be registered in the eCRF in the concomitant section.

Any changes in medicine during the test period must be reported in the concomitant section in the eCRF.

Any kind of antibiotic treatment is not allowed from inclusion through the test period, as this can influence the bacteria type and level investigated on the catheters.

#### **7.5. Supplementary materials and equipment**

The investigational device must be used with a lubricating gel, and subjects will be supplied with Optilube, sterile lubricating gel, which is CE-marked. Furthermore, the catheter will be cleansed after use according to the IFU with a Milton cleansing solution (CE-marked), and subjects will be supplied with this as well.

### **8. Risk – benefit analysis and ethical considerations**

#### **8.1. Risk-benefit analysis of the investigational device**

A risk analysis according to ISO 14971 Application of risk management to medical devices has been conducted. Risks have been proven minimized or eliminated through appropriate design control, confirmed by pre-clinical bench, laboratory, and clinical testing.

All unacceptable risks related to the device have been mitigated as far as possible and have been deemed acceptable for the clinical study. The CLINY catheter device is already CE marked.

#### **8.2. Risk-benefit for subjects participating in the clinical investigation**

The investigation is conducted in accordance with current law and applicable standards. (Section 15, Statement of Compliance), and in accordance with 'The Declaration of Helsinki', 1964, last amended at the 64th WMA General Assembly, Fortaleza, Brazil, October 2013, and ISO 14155 and the Medical Device Directive/Regulation.

The rights, safety and well-being of human subjects shall prevail over the interest of science or society.

The risks in this investigation are considered equal to the use of similar reusable catheters on the market and include haematuria, mechanical trauma, and risks of UTI. Please also see Adverse events, adverse device effects and device deficiencies section 18.

There is no known interaction between the use of the investigational device and the medication participants can take. Disadvantages of testing (trial engagement) may be the time spent on visits, adjustment to new catheter type and routine and responding to questions.

The catheterizations of the subjects with the investigational device will consist solely of self-catheterization, performed by experienced users. Prior to the first catheterization, the users will receive instructions from urology nurses or PI at an investigational site with many years of experience in conducting IC.

There are no direct benefits for the subjects involved. However, potential benefits for the subjects in this investigation may include decreased fear of 'running out', i.e., minimizing the worry about continuous access to catheter. By participating in this investigation, the subjects will contribute with important information with respect to reuse of catheters, and how that practice might influence QoL and catheter hygiene.

#### **8.3. Risk Analysis for the conduct of the clinical investigation**

A risk assessment of the clinical investigation will be conducted initially prior to the first subject enrolment and periodically re-assessed based on any new risks identified through the process. This assessment will be completed throughout the duration of the investigation, as defined by the study team. A risk-based monitoring strategy may be implemented including on-site remote, and central monitoring. Details of the strategy are defined in the monitoring plan.

#### **8.4. Delegation of responsibility**

Before initiation of the clinical investigation, sponsor must be provided with key site personnel signed and dated curriculum vitae (not more than 2 years old) to verify their qualifications. Key site personnel are those, who treat

or evaluate subject data in the clinical investigation. Also, the sponsor will ensure that all site personnel are trained in the investigation procedures, how to complete the case report forms (CRF's), procedure for reporting an adverse event (AE) or serious adverse event (SAE) or adverse device effects (ADE) or serious adverse device effects (SADE) (how, when, to whom), and who to contact in case of emergency related to the investigational device. All training and delegation of tasks will be documented in the Clinical Investigation Training log and the Site Personnel Signature and Delegation log.

## **9. Monitoring Plan**

The sponsor is responsible for ensuring appropriate monitoring of the clinical investigation activities as described below. This study specific monitoring plan includes details regarding the monitoring strategy (i.e., onsite, remote, and centralized).

The monitor will be the primary contact for the PI and delegates.

Monitoring activities are mandatory as per good clinical practice, however the extend and depth of these activities depend on the criticality of the clinical investigation, speed of enrolment, the experience of the clinical investigation personnel in carrying out clinical investigations and specific study designs.

For the purpose of this clinical investigation the below described monitoring procedures have been selected.

The data collected throughout the investigation and the conduct of the investigation, will be monitored per the monitoring plan to ensure, and verify, that the rights and well-being of the subjects are protected, that the reported data are accurate, complete, and verifiable from source documents, and that the conduct of the investigation complies with the approved CIP, subsequent amendment(s), ISO14155 and the applicable regulatory requirement(s).

The monitoring process is described below.

The monitoring in this investigation will be conducted periodically at all sites by the Clinical Manager.

The investigator must be available for and agrees to cooperate with Coloplast Clinical Managers (CM) during their visits and ensure that they have direct access to all documents that they require, including direct access to the subject's files.

The investigation will be subject to internal audits if relevant. All monitoring visits and possible audits will be followed by internal reports and corrective actions, if needed.

Follow-up letters will be forwarded to sites after all visits and any findings should be addressed by the investigator or delegate.

To ensure proper conduct of the investigation the following visits on site will be performed before/during the investigation:

- Site selection visit
- Site initiation visit
- Periodic monitoring visits
- Close out visits

### **9.1.1. Site selection visit**

Depending on the prospective clinical investigation and sites experience with the specific investigational device, an on-site qualification or site selection visit shall be performed during which the feasibility of the clinical investigation requirements will be discussed. A common agreement between sponsor and Principal Investigator shall be reached. This visit may also be replaced by one or more phone calls or remotely, using Microsoft Teams, Skype, or Face Time, if the Principal Investigator is known to the sponsor or if the site is restricting visitors due to the Covid-19 pandemic.

### **9.1.2. Initiation visit**

An initiation visit with full training on all aspects of the clinical investigation will be provided.

The initiation visit will be held as a physical meeting or remotely using Microsoft Teams, Skype or Face time and the visit will be held as close to study start as possible.

Before initiation of the clinical investigation, sponsor must be provided with key personnel signed and dated curriculum vitae (not more than two years old) and documentation of current ISO14155 training (within the last two years) to verify their qualifications.

All clinical investigation sites will complete an initiation visit during which full training on all aspects of the clinical investigation will be provided including training in handling of the investigational test product, the CLINY Self-Catheterization Set. This visit can also be conducted on-site or remotely if the site is restricted visitors due to the Covid-19 pandemic.

### **9.1.3. Monitoring visits**

The sponsor shall determine the extent and nature of monitoring appropriate for the clinical investigation based on the risk assessment. The sponsor shall ensure, through oversight of the clinical investigation and timely adverse event reporting, that unanticipated adverse device effects are identified and investigated rapidly so that, where necessary, additional risk control measures can be implemented.

The monitor is to ensure adherence to the clinical investigation plan, the safety of the subjects, accurate data recording on the e-CRFs and to monitor recruitment rates and adherence to follow-up schedules. During the clinical investigation, monitors shall check that appropriate written informed consents have been obtained. The Principal investigator shall permit and assist the monitor to carry out verification of completed eCRFs against data in the source documents.

The Principal Investigator can delegate tasks to his/her collaborators, however the roles and responsibilities as time of involvement for each clinical site personnel must be documented on the Site Personnel signature and Delegation list as well as training received before getting involved with the clinical investigation must be documented in the Clinical Investigation Training Log.

The monitor shall inform the sponsor about any problems relating to facilities, technical equipment, or medical staff at the clinical investigation site. The monitor shall also be responsible for notifying such deficiencies in writing to the Principal Investigator and convene with the clinical investigation site personnel appropriate and timely corrective actions.

The sponsor, or delegate, will provide clinical monitoring, including review of eCRF with verification to the source documentation, as defined later in this monitoring plan.

Before doing any review of subject data, the monitor must review the signed Informed Consent Forms and only monitor data from subjects with a correct signature on these forms. The monitor shall also be responsible for notifying such deficiencies in writing to the investigator and convene with the clinical investigation site personnel appropriate and timely corrective actions.

The first monitoring visit at the site should be conducted as soon as reasonably possible after the first subject(s) has(have) completed the first visit of the investigation. This is to minimise systematic errors done by site and to clarify potential questions before proceeding with enrolment of more subjects.

Additional monitoring will be conducted in accordance with the recruitment rate or if there is a need for more frequent visits upon request from site or Clinical Manager.

The Investigation Site File shall be monitored for 100% completion per the Investigation File Requirement Checklist. Monitoring activities will be documented in a site visit report. A follow up summary describing the observations, including documentation of any deviations and actions required shall be provided as soon as reasonably possible to the Principal Investigator and/or delegate after the conducted monitoring visit.

All data collected can be directly entered in the eCRF. The monitor will by edit checks ensure that all fields are completed in the eCRF. Monitor will ensure by closely monitoring, that all queries are timely resolved.

The sponsor representative (Clinical Manager) will have close contact to the site in the recruitment period to ensure that any concerns, problems, or recruitment challenges are solved with the site in a timely manner.

Only the Principal Investigator, delegated site personnel and the sponsor representatives will have access to all the eCRF records.

### **9.2. Source data verification**

Source data is all information in original records, certified copies of original records of clinical findings, observations, or other activities in the clinical investigation, necessary for the reconstruction and evaluation of the clinical investigation. This includes source data initially recorded in an electronic format. A source document is a document in which data collected for a clinical investigation is first recorded.

All documents and data related to the clinical investigation handled by site personnel, shall be produced, and maintained in a way that assures reliability, integrity, control, and traceability, and shall be appropriately stored to provide a complete history.

The Principal Investigator shall assure the accuracy, attribution, completeness, legibility, and timelines of the data reported to the sponsor in the eCRFs and in all required reports. All printed copies of electronic source documents shall be certified, as indicated by a dated signature by the investigational site personnel at the time the document is printed. Special requirements should be applied to the capture, review, and retention of electronic source data, to ensure reliability, quality, integrity, and traceability.

The data reported in the eCRF shall be derived from source documents and be consistent with these source documents, and any discrepancies shall be explained in writing. The eCRF can serve as the source document and this must be documented on the Source Data Specification Form. The Source Data Specification Form must be completed at the initiation visit detailing the location of the source data for each data point agreed upon by the Principal Investigator.

Data points for data verification:

- Infomed Consent Form
- In- / Exclusion criteria
- AE/ADE/SAE/SADE/DD
- Other

Written informed consent, in- and exclusion criteria and all AE's, ADE's, SAE's, SADE's and DD occurring in the investigation will be 100% verified for timely completion for all subjects enrolled in the investigation.

### **9.3. Remote monitoring**

Remote or centralized monitoring is a remote evaluation carried out by sponsor personnel or representatives (e.g., data management personnel, statisticians, or clinical monitors) at a location other than the site(s) at which the clinical investigation is being conducted. Remote monitoring processes can provide many of the capabilities of on-site monitoring as well as additional capabilities.

In addition to onsite monitoring visits, remote monitoring of the data entered in the eCRF system could be used to achieve the following:

- Conduct activities such as: standard checks of range, consistency, and completeness of data and checks for unusual distribution of data, such as to little variance.
- Special attention will be given in case of frequent data anomalies or errors, protocol deviations/violations or excessive dropouts.
- Augment on-site monitoring by performing monitoring activities that can only be accomplished using centralized processes (e.g., statistical analyses to identify data trends not easily detected by on-site monitoring).
- Monitor data quality through routine review of submitted data in real-time to identify missing data, inconsistent data, data outliers, and potential protocol deviations that may be indicative of systemic and/or significant errors in data collection and reporting at the site.
- Verify source data remotely, provided that both source data and eCRF's can be assessed remotely.

- Conduct aggregate statistical analyses of the study data for plausibility and completeness.
- Conduct analyses of site characteristics, performance metrics (e.g., high screen failure rates, high frequency of eligibility violations, and delays in reporting data), and clinical data to identify early on corrective actions needed for characteristics correlated with poor performance or noncompliance.

## 10. Statistical considerations

### 10.1. Statistical design, method, and analytical procedures

Baseline assessments and endpoints will be reported by descriptive statistics and/or listed. Summaries will be presented by device i.e., IC and re-use catheters and if relevant, by other grouping variables.

Descriptive statistics for continuous variables are presented with N, Mean, SD (standard deviation), Median, Min and Max, where N denotes the number of subjects contributing with non-missing data. For discrete variables, descriptive statistics are presented with N and percentage, where percentage is based on the total number of subjects/observations with non-missing data.

All statistical analysis will be performed with [REDACTED]

### 10.2. Definition of analysis populations

Screening Failures (SF), Intention to Treat (ITT), Full Analysis Set (FAS) and Safety populations will be defined at a formal data review meeting prior to database lock. As a minimum, the data management specialist, the clinical manager, and the statistician will be involved in the classification of subjects.

Subjects not adhering to inclusion and/or exclusion criteria are considered screening failures (SF).

The Safety population will constitute all subjects enrolled i.e., subjects who have given informed consent.

The full analysis set is a modified ITT population i.e., a sub-population of the ITT population, and will constitute all subjects enrolled, who have been exposed to at least one device, with at least one endpoint recorded (data non-missing).

Individual endpoints/data points may be excluded from the analysis, even though the corresponding subject belongs to any of the pre-defined populations. Exclusion of subjects or data points must be documented.

All statistical analysis will be based on the full analysis set, whereas adverse events and device deficiencies will be assessed in the safety population.

### 10.3. Analysis of the primary endpoint

HR-QoL index score will be analysed in mixed model with subject included as a random component and catheter (IC and re-use catheters) included as a systematic effect.

Evidence of significant effect will be concluded, if the 95% confidence interval of the difference between IC and re-use catheters, do not include zero.

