**Figure 2: Design of the Clinical Investigation**

### 5.2. Primary endpoint

**Primary endpoint:**

- Health-related quality of life (HR-QoL) measured by intermittent self-catheterization questionnaire, (ISC-Q) index score at Baseline Visit (V1) and at the termination Visit (V5)

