## **6. Clinical Investigation population**

The clinical investigation will be conducted in 40 subjects enrolled in multiple clinical investigation sites. The enrolment is competitive.

To allow for statistically significant data, a minimum of 20 eligible completed subjects in multiple clinical investigation sites will be adequate for obtaining indications on the effects of repeated reuse of catheters, hence the aim for this investigation is 20-40 completers.

Considering a drop-out rate of 50 %, the total number of subjects to be enrolled must be 40.

Recruitment and discontinuation will be followed very closely, and all replacements evaluated on an ongoing basis depending on both number of discontinued subjects and the time the subjects participated in the investigation. As a minimum sponsor will make a status on the recruitment strategy every month or at least when half of the subjects have been recruited.

The aim is to keep the LPO date. If concerns of high dropout rate recruitment/retention arise and status will be discussed by sponsor.

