## 10.6. Level of significance and power

A significance level of alpha 0.05 (2-sided) will be applied.

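### The primary model, read in the standard way, assumes equal variance for single-use and CLINY scores; if V5 scores are missing and the SDs differ, the 95% CI is miscalibrated

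*Combined protocol and SAP*

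**What the plan says.** The primary endpoint (section 5.2) is the ISC-Q "index score at Baseline Visit (V1) and at the termination Visit (V5"), so each subject has at most two scores: V1 for single use and V5 for CLINY. Section 10.3 has the score "analysed in mixed model with subject included as a random component and catheter (IC and re-use catheters) included as a systematic effect", and sets the only inferential rule in the plan: "Evidence of significant effect will be concluded, if the 95% confidence interval of the difference between IC and re-use catheters, do not include zero". Section 10.6 adds: "A significance level of alpha 0.05 (2-sided) will be applied". No residual covariance, degrees-of-freedom method or missing-data method is stated.

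The full analysis set (section 10.2) takes enrolled subjects "who have been exposed to at least one device, with at least one endpoint recorded (data non-missing"). A V1 ISC-Q score is a recorded endpoint, so an exposed subject without a V5 score stays in the model.

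On numbers, section 6 says that "a minimum of 20 eligible completed subjects in multiple clinical investigation sites will be adequate" and continues: "Considering a drop-out rate of 50 %, the total number of subjects to be enrolled must be 40". Section 5.1 has early terminators attend V5 with its full set of assessments. Section 6.3 wants V5 done promptly after withdrawal for antibiotic treatment. Section 10.5 says that discontinued subjects will be asked to complete V5.

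**The concern.** One random subject effect plus one fixed catheter effect, with nothing further stated, is normally fitted as compound symmetry: a common variance at V1 and V5, and a single correlation that also serves as the regression slope of V5 on V1. When every subject has both scores, this is the paired t-test whatever the two SDs are. When V1-only subjects are included, two things change. The pooled variance is weighted towards V1, so the standard error is wrong if the V5 SD differs. And the missing V5 scores are in effect predicted from V1 with a slope that ignores the SD ratio, which biases the difference if those lost have unusual V1 scores.

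Unequal SDs are plausible, though not documented: V1 rates a product the subject already uses, and V5 rates a new one that some may like and others reject. At stake is the calibration of the one interval from which the plan will conclude significance.

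**Working it through.** **Inputs from the documents.** 40 enrolled, minimum 20 completers, 50% drop-out (section 6); two-sided alpha 0.05 (10.6); model and CI rule (10.3); V1-only subjects retained (10.2).

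**Inputs assumed, because none is given.** V1 SD = 1, SD ratio CLINY/single use 0.67 to 2, correlation ρ 0.3 to 0.7, and either random loss of V5 or loss more likely at high V1.

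**Step 1, the plan's figure.** 20/(1 − 0.5) = 40, which matches section 6.

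**Step 2, the estimator.** With n V1 scores and m pairs, and the difference taken as CLINY minus single use:

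D = mean V5 (completers) + b × (mean V1 of all − mean V1 of completers) − mean V1 of all.

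The correct slope is β = ρ × SD5/SD1; the common-variance model uses its one estimated correlation as b. With m = n the b term vanishes, leaving the paired difference.

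**Step 3, the attainable SE under random loss.** With the correct slope, Var(D) = SD5²(1 − ρ²)/m + (ρ·SD5 − SD1)²/n. At SD ratio 1.5, ρ = 0.5, m = 20, n = 40: 2.25 × 0.75/20 + (0.75 − 1)²/40 = 0.0844 + 0.0016 = 0.0859, so SE = 0.293. The common-variance model reports 0.259 on average.

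**Step 4, simulation.** 40 subjects, 4,000 trials per scenario, REML random-intercept fit, t interval with df = completers − 1; Monte Carlo error of coverage is 0.3 to 0.6 points. With no V5 missing, coverage is 94.6–95.5% at every SD ratio from 0.67 to 2. With 20 of 40 V5 missing and ρ = 0.5:

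| SD ratio | Random loss: model SE / true SE | Coverage | V1-related loss: bias (V1 SDs) | Coverage |
|---|---|---|---|---|
| 1.25 | 0.230/0.252 = 0.91 | 93.9% | −0.08 | 92.3% |
| 1.5 | 0.259/0.294 = 0.88 | 92.7% | −0.14 | 89.2% |
| 2 | 0.322/0.408 = 0.79 | 89.3% | −0.29 | 82.1% |

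Under random loss the bias is about zero. With an unstructured 2×2 covariance, over SD ratios 1.25 to 2 with half of V5 missing, coverage is 94.7–95.9% (random) and 94.9–95.9% (V1-related), and bias is at most about 0.011 V1 SD.

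**Step 5, the slope explains the bias.** Take ratio 1.5, ρ = 0.5, V1-related loss; β = 0.75. The completers-only paired difference is biased by +0.106, which equals (1 − 0.75) × gap, so the V1 gap between all subjects and completers is 0.106/0.25 = 0.42 SD. The planned model's bias is −0.139 = (b − 0.75) × 0.42, so b ≈ 0.42 instead of 0.75.

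**Step 6, selection strength and fewer missing scores (ratio 1.5, ρ = 0.5).**
- 20 missing, stronger link to V1: coverage 85.8–86.6%; bias −3.0 points on an assumed V1 SD of 15, or −0.20 SD.
- 12 missing: 93.7% (random), 91.3–91.4% (V1-related).
- 10 missing: 94.5% (random), 93.7% (V1-related, weaker link).
- 6 missing: 93–95%.

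**Step 7, the opposite case.** At SD ratio 0.67 with 20 missing at random, coverage is 96.3–97.6%, so the CI is too wide. With V1-related loss the bias changes sign (+0.06 to +0.10 SD) and coverage is 89.5–93.1%.

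**The case against.** A reader might infer that half the V5 scores will be missing and that the interval is therefore too narrow. The documents do not support that. The 50% is a drop-out allowance, and drop-out is not the same as a missing V5 score: sections 5.1, 6.3 and 10.5 all seek a V5 assessment from early terminators. Twenty missing is a ceiling. It is not an empty concern, because section 10.5 only asks, section 6.3 foresees loss to follow-up, and section 10.2 allows single data points to be excluded. Replacing those who stop before day 14 does not help, since nothing removes the replaced subject's V1 score from the analysis set.

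Nor do the documents show that CLINY scores vary more, or that high V1 scorers leave more often. The lowest coverage found, 74.0%, needs half of V5 missing, a doubled SD, correlation 0.7 and V1-related loss together, and should not be read as the likely size. Section 10.3 is also silent on residual covariance, so equal variance is the standard reading rather than an explicit requirement.

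The study is exploratory, with no pass/fail criteria (sections 3.2 and 10.7). That limits the consequences. Yet section 10.3 still declares significance from this interval, and section 21 reserves the data for reimbursement or regulatory use.

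**Conclusion.** The point holds conditionally. Both missing V5 scores and unequal SDs are needed for the variance problem; bias needs, in addition, loss related to the scores. Under SD ratio 1.5 and correlation 0.5, the shortfall from nominal 95% coverage is 1 to 2 points with 12 to 20 scores lost at random. With V1-related loss it is about 4 points at 12 missing and 6 to 9 points at 20, depending on the assumed selection strength. With 6 missing it is at most 2 points, and with complete pairs there is none. All SDs, correlations and loss mechanisms here are assumptions. This is a modest weakness in the plan's only inferential rule that is cheap to remove before database lock; it does not make the planned analysis invalid in general.

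**What to change.** In section 10.3, specify a repeated-measures mixed model for the ISC-Q index with catheter as fixed within-subject factor, an unstructured 2×2 within-subject covariance (separate variances for single use and CLINY), REML, and Kenward-Roger degrees of freedom. Report the estimated V1–V5 correlation beside the SDs by device that section 10.1 already provides. The simulated unstructured analysis used a closed-form likelihood estimate rather than a Kenward-Roger fit, so its coverage figures are a close guide to the proposed analysis, not an exact result for it.

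Restricting to complete pairs is not an equivalent remedy: with equal SDs, correlation 0.5 and 20 scores lost in relation to V1, the paired t-test covers only 85.8%.

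The unstructured model does not correct loss driven by the unseen CLINY score. Appendix E lists drop-out reasons such as inconvenience and discomfort, so this is a real possibility. Add one simple sensitivity analysis, for example shifting the predicted CLINY scores of subjects without V5 over a stated range and reporting where the conclusion changes.

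Cost: a few lines of text and no new data. If the variances are equal and loss is random, the SE rises about 1–4%; with 20 pairs and an assumed SD of 15, from 3.53 to 3.65 (3.65/3.53 = 1.03) at correlation 0.3. With equal variances and 20 scores lost in relation to V1, the rise is larger: 0.231/0.206 = 1.12 in the Step 4 setting at correlation 0.5, and about 23% under a strong link.
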